The goals of therapy in bronchiolitis are to maintain tissue oxygenation, detect respiratory failure, and provide adequate hydration. Previous studies suggest approximately a third of patients hospitalised for bronchiolitis require fluid replacement^{8,9}.

Depending of the degree of disease severity, fluid replacement in patients with bronchiolitis who cannot maintain hydration orally can be accomplished by enteral or parenteral routes¹⁰. Nasogastric fluids are a form of enteral hydration that is commonly used in infants with bronchiolitis and forms part of our hospitals' bronchiolitis guideline, as well as international guidelines ^{10,11,12}.

The efficacy and use of nasogastric fluids in patients with bronchiolitis has previously been assessed in several studies.

- A survey of Australasian Paediatric Emergency Physicians by Oakley et al demonstrated that 48% of Emergency Physicians had used nasogastric fluids for patients with bronchiolitis¹⁷. Oakley et al extended their work to perform a retrospective cohort for patients less than 2 months of age with bronchiolitis amongst 3 paediatric centres over 3 bronchiolitis seasons¹⁹. Of those that required feeding support, almost 70% went on to have nasogastric fluids and on average spent 15 hours less in hospital than those that required intravenous fluids. A follow-up multi-centre randomized control trial was performed with patients between 2-12 months with bronchiolitis over a 2.5 year period and demonstrated a non-clinically important difference of 4.5 hours in length of stay between infants receiving nasogastric or intravenous fluids¹⁹.
- Kugelman et al performed a randomized pilot study in Israel with patients receiving either nasogastric fluids (of breastmilk of formula) or intravenous fluids and found that there was a non-statistically significant improvement in length of stay of approximately 21 hours for those receiving nasogastric fluids compared with those receiving intravenous fluids ...
- A study by Brand & Vaessen-Verbene in the Netherlands showed that 96% of paediatricians surveyed had used nasogastric fluids in their practice of treating patients with bronchiolitis¹⁵.
- A case series by Vogel et al in New Zealand studied 409 infants admitted to hospital with bronchiolitis, of which 21% received nasogastric fluids¹⁶.

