If consent is received, the patient will then be randomised to receive their nasogastric fluids at either a continuous rate or via intermittent boluses.

A block randomization strategy will be employed using the ralloc command of the statistical software Stata 15. Randomizations will be provided in consecutively numbered opaque sealed envelopes.

Blinding and allocation concealment

Due to the nature of the interventions assigned to each group, blinding of participants and the research assistant is not feasible. However, once outcome data is collected and recorded by the research assistant, the final data set will be further coded in such a way as to deidentify which nasogastric fluid regime patients were assigned to, further ensuring that the statistician analysing the results is blinded to the patients allocation .

e. Consent

Due to the age of patients in the trial, consent will need to be obtained from the patients' parent/s or guardian.

A dedicated research assistant will be responsible for providing the study consent and information form to eligible patients, as well as obtaining consent to minimise any conflicts of interest. However, in cases where the decision to initiate nasogastric fluids occurs when the research assistant is not available (such as after-hours), this role will be performed by the patient's treating clinician or nurse.

We will mitigate the risk of coercion by providing clinical staff with training around consenting procedures for the trial, ensuring that parents and guardians will be made aware that participation in this study is completely voluntary and that refusal to participate or withdrawal from the study will not affect their child's clinical care in any way.

The information sheet provided to parents/guardians will encompass a simplified lay version of the current evidence regarding nasogastric fluid therapy in bronchiolitis, the purpose of the NOBRO study and its' methodology. The information leaflet will specify our hospitals practice regarding the use of nasogastric fluids in patients with bronchiolitis, and that all patients within the study will be managed in line with best practice as noted by the PREDICT Australasian Bronchiolitis Guideline¹². The information sheet will also contain important information regarding patient confidentiality and disclosure of information. The information sheet will also include contact details of the investigating team and the hospitals Ethics association.

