 - We have defined this adverse event as when a patient experiences a sudden increase in any of the following that occurs persistently during, or within an hour after the patients nasogastric fluid regime has commenced
 - Heart rate >20 above baseline
 - Respiratory Rate > 10 above baseline
 - Work of breathing
 - Oxygen requirement

Both nasogastric fluid regimes are essentially treatment as usual, so we expect that the study as a whole poses no foreseeable additional risk to patients. We will still perform safety analysis on the pilot data collected.

We do not anticipate any significant difference in safety between the interventions. If we do detect a significant difference in safety, we will have procedures in place to address this for the subsequent larger study.

There is no evidence in the literature to suggest that patients receiving nasogastric fluids are at risk of a serious adverse event (SAE), such as

- death during the study period
- electrolyte disturbance causing seizure
- Any other event not mentioned above that is life threatening or jeopardises the patient or requires medical or surgical intervention

We will endeavour to manage any serious adverse events with the following practice:

- SAEs need to be reported within 24 hours by telephone to the local site investigator.
- The local investigator must report the SAE to their local ethics committee within 48 hours (or in accordance with local ethics committee regulations).
- The local investigator must also report SAEs to the principal investigators who will report the event to the Data Monitoring Committee chairman.
- The principal investigator will also report the SAE to all Ethics Committees and other regulatory bodies involved in the trial as per regional regulatory requirements.
- SAEs will also be reported to the consultant of the child's treating team. The medical consultant will initiate appropriate management and inform the family if the family is not already aware of the event. This reporting is the responsibility of the site investigator

g. Participant Withdrawal Procedures

Parents/guardians of any patient enrolled in the trial are able to withdraw their consent at any point after it is initially obtained either verbally or through written means. At the point of withdrawal of consent, the treating clinician will determine the course of ongoing therapy for the patient in discussion with the patients' parent/guardian as per normal practice.

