As this is a pilot trial, we aim to assess a range of outcomes to determine the feasibility of progressing with a subsequent larger randomized control trial

- As part of this pilot trial we aim to recruit more than 80% of eligible patients, determine the
 appropriateness and variance of our primary outcome and to further help us determine the
 sample size needed for our subsequent randomised control trial
- Estimation of our recruitment rate
- Retention rates for those in the intervention groups
- Determine the incidence of adverse events
- Auditing the completeness of data reporting
- The primary investigator will collect field notes and reflections on the study process, including aspects such as
 - o Identifying the willingness of clinicians to recruit patients
 - o Estimation of cost and resources
 - o Identification of any major issues with the study process

As part of this pilot we are also collecting data for all the intended outcomes for the larger trial to fully test the study procedures and data collection but will not use them for formal analyses. These other outcomes include:

- Time taken for the patient to return to adequate oral feeding after the introduction of nasogastric fluids. This is the primary outcome for our subsequent larger trial.
- Length of stay (in hours).
- The incidence of adverse events that may be attributed to nasogastric fluid therapy, including
 - Vomiting
 - o Pulmonary aspiration of nasogastric fluids
 - o Worsening of the patients respiratory status
- The number of infants requiring re-instatement of nasogastric fluids after nasogastric fluids are initially ceased
- The number of infants requiring a change from Nasogastric to intravenous fluid hydration
- The duration of supplemental oxygen requirement
- The need for admission to an Intensive Care Unit

i. Data Collection

A research assistant will be responsible for collecting relevant demographic and outcome data. Reidentifiable, coded patient information data will initially be recorded by the research assistant onto NOBRO study source document. The research assistant will then input this data into an Excel Spreadsheet. This spreadsheet will be password-protected and be located on a dedicated computer that only the research assistant has access to.

Following merging, identifiable data shall be made non-identifiable. The NOBRO study source documents will also be stored in a locked drawer in the research assistant's office.

k. Data Storage and Confidentiality

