Information collected from the study will be disposed of 5 years after the youngest patients' 18th Birthday. Any electronic records relating to study data will be deleted and paper records will be placed into appropriately labelled shredding bins

I. Data Analysis and Statistical Considerations

No formal hypothesis testing will be completed, as this is a pilot study. Descriptive statistics will be used to measure the various outcomes of the trial- e.g. data completeness, % eligible patients approached, % eligible patients approached who then consented, total number of eligible patients per week. Data analysis will be done using Microsoft Excel in consultation with the biostatistician.

Data analysis in this pilot study will primarily be related to determining an appropriate sample size and analysis methods for the subsequent RCT. Data will be collected over a 2 month period during which we anticipate to recruit 30 participants based on the current bronchiolitis presentation rate.

The primary outcome measure will be time to adequate oral feeding (TAOF) as detailed above. Descriptive and graphical statistics will be used to ascertain the nature of the frequency distribution of TAOF. Understanding the nature of the distribution of TAOF will inform the most appropriate analysis method to be used in the RCT. If the distribution is normal, or can adequately be transformed to normality, the standard deviations (SDs) of TAOF in each treatment group along with means will be calculated. The SD estimates may then be used to estimate the sample size required in the RCT. The other requirement for this sample size estimation is an understanding of what the minimal clinically important difference (MCID) in TAOF is. As this is a new and specific measure, clinical members of the team will use this preliminary TAOF data to determine a consensus MCID for TAOF. Given this information, preliminary analyses will be undertaken to detect any difference, if any, in TAOF.

Similar analyses will be undertaken with respect of secondary objectives, hospital length of stay, and tolerability though these will not inform sample size. With respect to tolerability, this preliminary data will be used to assess possible tolerability indices that may be used in the main RCT.

At the end of the pilot, a qualitative judgement will be made by all investigators as to whether the it is appropriate to proceed, in line with Abbott $(2014)^{23}$:

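### The MCID for TAOF is to be agreed from pilot data after arm-level results are calculated, and a search for a between-arm difference then conflicts with the ban on formal testing

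*Protocol*

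**What the plan says.** Section 3.l (Data Analysis and Statistical Considerations) opens with the rule "No formal hypothesis testing will be completed, as this is a pilot study". Section 3.i (Outcome Measures) says that the outcomes intended for the main trial, with TAOF listed first, are collected "to fully test the study procedures and data collection but will not use them for formal analyses".

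Section 3.l then sets out a sequence:

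1. If TAOF is normal or can be transformed to normality, its mean and SD are calculated in each treatment group. The SDs may feed the main trial's sample size.
2. Because TAOF is a new measure, "clinical members of the team will use this preliminary TAOF data to determine a consensus MCID for TAOF".
3. With that in hand, "preliminary analyses will be undertaken to detect any difference, if any, in TAOF". Similar analyses follow for length of stay and tolerability, with the qualification that these will not inform sample size.

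The Background (section 1) lists identifying a clinically important difference among the reasons for running the pilot. Section 3.f (Risk Mitigation Procedures) plans a safety analysis of the pilot data and describes what follows "If we do detect a significant difference in safety".

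**The concern.** There are two linked problems.

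**Source of the MCID.** A minimal clinically important difference is a judgement about what would matter to infants, families and clinicians. Outcome data by arm cannot supply it. As the steps are ordered, the people making the judgement may already know which arm did better and by how much. The only masking described (section 3.d) is the coding of the data set for the statistician. It does not cover the clinicians, and coded arm labels would not hide the size of a difference. The main trial's sample size varies with the inverse square of the target difference, so anchoring on a noisy estimate is costly.

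**Whether to test.** The protocol rules out formal testing and formal analysis of these outcomes, then asks for analyses whose stated purpose is to detect a difference, and speaks of a significant difference in safety. An analyst cannot tell from this text whether to run tests. With a sample this small, tests would have little power, and non-significant results could be misread as evidence of similarity.

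**Working it through.** The protocol gives no alpha, power, effect size or SD, so there is no calculation to reproduce. Its one figure is a recruitment expectation: data are collected over two months "during which we anticipate to recruit 30 participants based on the current bronchiolitis presentation rate".

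**Inputs**
- Total of 30 infants: section 3.l.
- Allocation ratio: not stated. The randomisation text says only that "A block randomization strategy will be employed using the ralloc command of the statistical software Stata 15". I assume 1:1, so 15 per arm.
- Two-sided alpha 0.05, main-trial power 90% (80% also shown) and a true difference of 0.5 SD: my assumptions, for illustration.
- Everything is in SD units, because the SD of TAOF is unknown.

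**Precision of the observed difference**
- SE = sqrt(2/15) = 0.365 SD.
- 95% half-width = t(0.975, 28 df) × SE = 2.048 × 0.365 = 0.75 SD.
- With no true effect, the observed absolute difference exceeds 0.5 SD with probability 2 × [1 − Φ(0.5/0.365)] = 17%.

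**Worst case, in which the MCID is set equal to the observed difference**
- With a true difference of 0.5 SD, the quartiles of the observed difference are 0.5 ± 0.6745 × 0.365, that is 0.254 and 0.746 SD.
- Main-trial n per arm = 2 × [(z for alpha + z for power)/d]². The sum of the z values is 1.960 + 1.282 = 3.242 at 90% power and 1.960 + 0.842 = 2.802 at 80%.

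| Target d (SD) | n per arm, 90% power | n per arm, 80% power |
|---|---|---|
| 0.254 (lower quartile) | 326 | 244 |
| 0.500 (truth) | 84 | 63 |
| 0.746 (upper quartile) | 38 | 28 |

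- A trial of 38 per arm would have about 58% power (two-sample t test) for the true 0.5 SD.

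**What a test in the pilot could show**
- Two-sample t test with 15 per arm: power 26% at 0.5 SD. A difference of 1.06 SD is needed for 80% power.
- Safety, two-sided Fisher exact test: 0/15 v 4/15 gives p = 0.10; 0/15 v 5/15 gives p = 0.042. Starting from no events in one arm, five events in the other (33 percentage points) is the first result below 0.05.

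**The SD, by contrast**
- With 28 pooled df, the 95% interval for the SD runs from sqrt(28/χ²(0.975)) = 0.79 to sqrt(28/χ²(0.025)) = 1.35 times the estimate. That is imprecise, but it is a legitimate use of a pilot and no part of this concern.

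**The case against.** The strongest defence is that the protocol never says the MCID will equal or follow the observed difference. TAOF is described as neither routine nor well published, and clinicians may reasonably want to see its scale and spread before judging what matters. The phrase about preliminary TAOF data may mean no more than that. Their use of arm-level results is inferred from the order of the sentences. This stands, and it makes the sample-size range above a worst case. What remains is that nothing confines the clinicians to pooled data, nothing places the consensus before the arm results, and no clinical anchor is named.

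A second defence is that preliminary analyses may be meant descriptively: no test, alpha or p-value is specified. That is a possible reading. But detecting a difference, and a significant difference in safety, are the language of testing, and no estimate with an interval is offered in their place.

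Three stronger readings are tempting and are not supported:

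- **A chance small difference would stop a worthwhile trial.** The progression judgement at the end of section 3.l turns on whether process problems can be overcome, not on effect size.
- **The MCID step is repeated for other outcomes.** Length of stay and tolerability are expressly kept out of the sample size, and no MCID is described for safety.
- **The 4.5 hours in the Background could anchor the MCID.** The cited randomised trial "demonstrated a non-clinically important difference of 4.5 hours in length of stay", but that concerns length of stay under nasogastric versus intravenous hydration. It is a different outcome and comparison, and gives no MCID for TAOF.

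**Conclusion.** The point holds in a limited form. The protocol lets the MCID for TAOF be agreed from pilot data once group means and SDs exist, with no safeguard against anchoring on the observed difference. It also gives conflicting instructions on whether the arms are to be tested against each other.

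The 0.75 SD half-width rests only on 30 infants split evenly. The range of 326 down to 38 per arm against 84 also requires full anchoring, a true difference of 0.5 SD and 90% power, none of which the protocol states. It should be read as the exposure left open, not as the plan's expected result. At 80% power the range is 244 down to 28 against 63, so the conclusion does not hang on that choice.

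This is a should-fix. It does not affect the pilot's participants or its feasibility aims. It does affect planning of the main trial, which is a central purpose of the pilot, and an MCID untouched by the arm results cannot be recovered once those results have been seen.

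**What to change.** 1. In section 3.l, state that the clinical team will agree the MCID for TAOF on clinical grounds before any arm-level TAOF is released, using at most the pooled, arm-blind distribution to understand its scale. Align the Background sentence that makes identifying this difference a reason for the pilot.
2. Keep the pilot SD as an input to the main trial's sample size.
3. Replace the sentence in section 3.l on detecting a difference in TAOF, and the phrase in section 3.f on detecting a significant difference in safety, with summaries by arm and the between-arm difference with its 95% CI. Label these as not for inference on efficacy or safety and not used to set the MCID. Treat length of stay and tolerability in the same way.

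The cost is a few sentences and one consensus meeting held earlier. The small downside is that the pilot reports no p-values, which is what the protocol's own rule against formal testing already implies.
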